4.2.2.1. Site-specific Modeling

We will consider refitting primary models for each site separately to explore the effect of site heterogeneity on our results.

Sample Size Considerations

The sample size of 160 participants (80 randomized to the intervention group and 80 randomized to the control group) provides greater than 90% power to detect difference in quality of life between groups (delta change =4) assuming a within-subject correlation of 0.8 and a standard deviation of the change in score equal to 9.5 based on our pilot data. The primary outcome was determined by our community partners.

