5.0 STATISTICAL CONSIDERATIONS

5.1 Outcome Measurements

None of the listed outcomes relate to safety.

Primary Outcome Measure

The specific key measurement used to measure the effect of the intervention corresponding to the primary outcome is change in health-related quality of life. The protocol aims primarily to detect a significant (5% significance level) between-group difference from baseline to 4 months (delta

change=4) assuming a within-subject correlation of 0.8 and a standard deviation of the change in score equal to 9.5 based on empirical evidence.

Secondary Outcome Measure

Patient satisfaction and activation will be explored using changes in the Patient Satisfaction with Decision Scale and Patient Activation Measure. Utilization will be measured evaluating comparisons of hospitalizations, emergency department, and referrals to hospice and palliative care. Advanced care planning will be measured by comparing rates of advance directive documentation, Physician Orders for Life-Sustaining Treatment, and goals of care documentation in patients' electronic health record charts. Patient survival will also be compared between groups. Total costs of care will be abstracted from UHH database only to conduct a budget impact analysis and obtain point estimates for refinement of the intervention in anticipation of a larger multi-center trial. A cost-effectiveness analysis is not planned and will not occur until effectiveness has been demonstrated in subsequent studies upon completion of this study.

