5.3 Sample Size

The primary goal is to improve quality of life. A total of 160 patients are needed to attain significant between-group differences from baseline to 4 months after study enrollment for patients. (See Primary Outcome Measure section above).

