4.2.1. Statistical Modeling

To assess our primary outcome of the effect of the intervention on change in health-related quality of life from baseline to 4-months post-enrollment between groups, we will calculate expected mean differences between groups by Generalized Estimating Equations (GEE) models where the outcome will be modeled as a function of treatment group, categorical time (baseline, 4 months, 12 months) and an interaction term between treatment group and time with an exchangeable correlation clustered within person. Significance will be assessed between groups overtime using a type III F-test on the interaction term. All ratios will be expressed as referent to the control group.

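### The SAP's power claim of more than 90% does not follow from its own inputs: an SD of change of 9.5 with 80 per arm gives about 75% at 4 months

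*Combined protocol and SAP*

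**What the plan says.** The primary outcome is the change in FACT-G from baseline to 4 months (protocol 5.1; SAP 3.1). The design inputs appear in two places.

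- Protocol 5.1, Primary Outcome Measure: "The protocol aims primarily to detect a significant (5% significance level) between-group difference from baseline to 4 months", with a difference of 4, "assuming a within-subject correlation of 0.8 and a standard deviation of the change in score equal to 9.5". It does not say whether the 5% is one- or two-sided.
- SAP, Sample Size Considerations (after 4.2.2.1): 80 per arm "provides greater than 90% power to detect difference in quality of life between groups (delta change =4"), with the same correlation and "a standard deviation of the change in score equal to 9.5 based on our pilot data".

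Protocol 5.3 states the same total without a power figure: "A total of 160 patients are needed to attain significant between-group differences from baseline to 4 months". The planned test is in SAP 4.2.1, for a GEE model with three categorical visits: "Significance will be assessed between groups overtime using a type III F-test on the interaction term". The power sentence does not say which test it refers to. Neither document gives a 12-month effect or an attrition allowance.

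**The concern.** For an unadjusted comparison of mean changes, four quantities fix the power: the difference, the SD of the change, the number per arm and the significance level. The plan gives all of these except sidedness, and they do not produce the stated power.

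The within-subject correlation is a clue to the cause. Once the SD of the change is known, the correlation adds nothing to an unadjusted comparison of changes. It is needed to convert the SD of a single score into an SD of change. Quoting 0.8 beside 9.5 therefore raises the possibility that 9.5 is a single-score SD with the wrong label.

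This is the only power statement for the only confirmatory outcome; the secondary outcomes are declared exploratory. How much weight a null result deserves depends on whether the design had roughly a 25% or a 1% chance of missing a 4-point difference, and the reader cannot tell which.

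**Working it through.** **Inputs.** n = 80 per arm, difference d = 4, SD = 9.5, correlation r = 0.8 (SAP Sample Size Considerations; protocol 5.1); 5% level (protocol 5.1). Two-sided is assumed and one-sided is also shown. Power is from the noncentral t with 158 df unless noted.

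**Step 1: the plan's figure, inputs as labelled (reading A, SD of change 9.5).**

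- SE = 9.5 × √(2/80) = 1.502
- d/SE = 4/1.502 = 2.663
- Power = 75.4% two-sided (75.9% by the normal approximation), 84.3% one-sided

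The stated figure of more than 90% is not reproduced. With complete data, the 4-month interaction term of the planned GEE is the same difference in mean changes, so this applies to it directly. At 80 per arm, 90% power would need an SD of change of 7.76 or less, or a difference of 4.9 points.

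**Step 2: the test in SAP 4.2.1.** The interaction over three visits has 2 df. Exchangeable correlation implies the same SD of change at both follow-ups and a correlation of 0.5 between the 4- and 12-month changes. With differences d4 and d12, the noncentrality is

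λ = (4/3) × (d4² − d4·d12 + d12²) / SE², where SE² = 2.256.

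| d4, d12 | λ | Power, F(2,158) |
|---|---|---|
| 4, 4 | (4/3) × 16/2.256 = 9.46 | 78.4% |
| 4, 0 | (4/3) × 16/2.256 = 9.46 | 78.4% |
| 4, 2 | (4/3) × 12/2.256 = 7.09 | 65.3% |
| 4, 5.2 | (4/3) × 22.24/2.256 = 13.14 | 90.6% |

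This test reaches 90% only if the 12-month difference is about 5.1 or more, or reverses to about −1.1 or lower.

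**Step 3: 9.5 as the SD of a single score (reading B).**

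- SD of change = 9.5 × √(2 × (1 − 0.8)) = 9.5 × √0.4 = 6.01
- SE = 6.01 × √(2/80) = 0.950; d/SE = 4.21
- Power for the 4-month contrast = 98.7% two-sided
- 2-df test: 99.4% for (4, 4), 97.0% for (4, 2)
- Detectable difference at 90% power: 3.1 points

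This agrees with a claim of more than 90%.

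**Step 4: other routes to 90% with the SD label kept.** SD of change 9.5 and r = 0.8 imply a single-score SD of 9.5/√0.4 = 15.02.

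| Comparison | SD used | Two-sided | One-sided |
|---|---|---|---|
| 4 months, baseline-adjusted | 15.02 × √(1 − 0.64) = 9.01 | 79.7% | 87.5% |
| Mean of 4- and 12-month changes | 15.02 × √(0.2 × 1.5) = 8.23 | 86.4% | 92.2% |
| Mean of both follow-ups, baseline-adjusted | 15.02 × √(0.9 − 0.64) = 7.66 | 90.7% | 95.0% |

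The last two rows assume a 4-point difference at both follow-ups. No 4-month version reaches 90%.

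**Step 5: missing 4-month surveys.** The loss rates below are assumed for illustration; n is reduced in the two-sided t-test.

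| Missing | n per arm | Reading A | Reading B |
|---|---|---|---|
| 10% | 72 | 70.9% | 97.8% |
| 20% | 64 | 65.7% | 96.2% |
| 30% | 56 | 59.8% | 93.7% |

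**The case against.** The strongest reply is that both the SD label and the power figure could be right if the calculation was for a different comparison. The power sentence names no time point or test, and the SAP plans a three-visit model. A baseline-adjusted comparison of the average of the two follow-ups has 90.7% power on the stated inputs, and it makes use of the 0.8. For the same reason, the quoted correlation is not proof of a mislabelled SD, because it also carries information when baseline is adjusted for.

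That much stands, and it is why the test behind the power figure must be named. It does not rescue the claim. The averaged comparison is neither the 4-month primary outcome nor the interaction test in SAP 4.2.1, and it needs a 12-month effect that the plan never states. Baseline adjustment at 4 months alone still falls short of 90%.

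It can also be said that if 9.5 is a single-score SD, the power claim is true, the margin is ample even with 30% of surveys missing, and only a label changes. That is correct, but nothing in the documents lets a reader choose that reading over the literal one. Finally, a null result will be judged largely on its confidence interval. This limits the harm but does not make the planning statement correct.

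**Conclusion.** The concern holds. For the baseline-to-4-month comparison, power above 90% and an SD of change of 9.5 are incompatible at 80 per arm. As written, power is about 75% two-sided or 84% one-sided, and about 65% to 78% for the planned 2-df test when the 12-month difference is 2, or is 4 or 0. If 9.5 is the SD of a single score, power is about 99% and the error is in the label.

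The result rests on complete data, equal arms of 80, and the plan's own difference and SD. The 2-df and single-score figures also use the stated 0.8 or the planned exchangeable structure. Which entry is wrong cannot be decided from the documents.

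**What to change.** Establish from the pilot data, which the SAP cites as the source, what 9.5 measures. Then correct one entry.

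- **If 9.5 is the SD of change:** restate the power in the SAP as about 75% for the 4-month between-arm contrast (two-sided 5%, 80 per arm), with a detectable difference of about 4.9 points at 90% power. Bring protocol 5.3 into line.
- **If 9.5 is the SD of a single score:** relabel it in protocol 5.1 and in the SAP, give the implied SD of change of 6.0, and state power of about 99%.

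In either case, name the test that the power figure refers to, say whether the 5% is two-sided, and give the power at the expected proportion of missing 4-month surveys. If the figure was meant for the 2-df test or for an average over both follow-ups, state the assumed 12-month difference and say that the figure is not the power of the 4-month contrast.

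The cost is wording in the SAP's Sample Size Considerations and protocol 5.1 and 5.3. Under the first option the stated power drops; under the second it stands. No additional enrolment and no change to the analysis is requested.
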